8.6 Interim Analysis

As the circulation of influenza viruses is seasonal and the rates of influenza are difficult to predict, this study is group sequentially designed with maximally 2 interim analyses planned over the course of the study. The goal of Interim analyses is, first, to minimize the risk of not being able to take a significant test decision after the end of the study, and second, to be able to stop the study for early evidence of efficacy or for futility after observing at least 50% of planned ILI-cases.

- If the number of RT-PCR confirmed influenza cases is less or equal to 119 overall, no interim analysis for efficacy and futility will be done and the study will be continued because the probability to make a conclusion for futility or efficacy is too low.
- If the number of influenza cases ranges equal to 120 but less than 238 unblinded interim analyses for efficacy and futility will be performed by an independent Data

Monitoring Committee (DMC). To maintain the overall 95% significance level ($\alpha = 2.5\%$, 1-sided) for primary objective testing, an error-spending-function will be used.

The benefit of using an error-spending-function is that no maximum number of analysis stages and the timing of the analyses need to be pre-specified, what in practice means that the duration of the study in terms of number of seasons can be left open. Error-spending function is applied to calculate α -boundaries, forming the adjusted probabilities for the type 1 error. If the p-value for primary objectives test is lower than the respective α -boundary the trial stops early (i.e. without reaching the targeted number of cases of 238) for efficacy. Similarly β -boundaries are calculated, i.e. the adjusted probabilities for the type 2 error β , and if the p-value is higher than the β -boundary, the trial stops early for futility at that stage. In other words the trials stops early for futility, when the data provides sufficient evidence that the alternative hypotheses is not true, i.e. that the test vaccine is not as good as expected. Otherwise, the trial continues enrolment. Decisions to stop or continue the trial will be made on the basis of discussions between the DMC and Sponsor's Senior Management.

- If the number of influenza cases is greater or equal to 238 (targeted number of cases to be able to evaluate the primary objective) the trial will be stopped, data will be unblinded and the final analysis will be performed by the Sponsor. If the trial proceeds to the final analysis (upon reaching 238 cases) the boundaries for acceptance or rejection are identical to the assumed type 1 and type 2 errors for the overall design, and the trial stops to either reject or not reject the null hypothesis of the primary objective.

In case DMC states that the observed data provides already the full information level needed for the final test decision, then the final analysis can be done on full alpha level and no further enrolment is needed. However if the decision of the group-sequential test is to continue the study then it is on the DMC to determine the number of subjects needed to be additionally enroled. The monitoring committee should not be influenced by the results of the efficacy testing at the interim analysis when planning further subjects' accrual or the times of future analysis. Only the overall number of cases is allowed to be used for further planning. The following formula for determination of sample sizes for further enrolment may be used:

$$N_{\text{total}} = (C_{\text{planned}} - C_{\text{observed}}) * 200 / (ER_{\text{aQIV}} + ER_{\text{Comp}}),$$

where N_{total} denotes the total number of subjects needed for further enrolment, C_{planned} is the overall number of cases needed for the test, i.e. 238 cases, C_{observed} is the number of cases observed at current stage, and ER are the respective ER s assumed for each treatment group, i.e. 1.4 for aQIV and 3.5 for non-influenza comparator. A drop-out rate of 10% should be added.

For the analysis of early stopping for futility and for efficacy, an error-spending function will be applied to provide statistical stopping rules for efficacy (α -boundaries) and futility (β -boundaries) for the first interim analysis and second interim analysis, if necessary, based on the information accumulated until that specific interim stage, i.e. based on the accumulated variance of the parameter of interest.

These boundaries will be calculated on a p-value scale (
<https://support.sas.com/documentation/onlinedoc/stat/131/seqdesign.pdf>)

At each interim stage, α -boundaries, forming the adjusted probabilities for the type 1 error, are calculated using error-spending function and if the p-value for the test of primary objective is lower than the respective α -boundary the trial stops for efficacy at this stage. Using the same error-spending-function applied on the overall type 2 error of 0.1 (Power 90%), β -boundaries are calculated, i.e. the adjusted probabilities for the type 2 error β , and if the p-value is higher than the β -boundaries, the trial stops early for futility at this stage.

In other words the trial stops early for efficacy if data collected at this stage allows to demonstrate primary efficacy objective (reject null-hypothesis); and the trial stops early for futility, if the data provides sufficient evidence that the test vaccine is not good as expected (the alternative hypotheses of absolute vaccine efficacy over the protocol-specified margin is not true, i.e $VE < 0.4$). Otherwise, the trial continues to the next stage and more subjects will be enrolled.

The cumulative O'Brien-Fleming type error-spending-function (Lan and DeMets, 1983; option ERRFUNCBOF in SAS® PROC SEQDESIGN) will be used for both α - and β -boundaries; the error-spending function is defined as:

$$E(t; \alpha) = \begin{cases} 1 & \text{if } t \geq 1 \\ \frac{1}{\alpha} 2 \left(1 - \Phi\left(\frac{z(1-\alpha/2)}{\sqrt{t}}\right)\right) & \text{if } 0 < t < 1 \\ 0 & \text{otherwise} \end{cases}$$

where α equals α for α spending function and β for beta spending function, and where t is the information fraction.

With a specified type 1 error, α , and information level t at stage k , the cumulative error is $\alpha E(t; \alpha)$ <https://support.sas.com/documentation/onlinedoc/stat/131/seqdesign.pdf>

If the trial proceeds to the final analysis, the boundary for rejection of null hypothesis is identical to the type 1 error (that is as the 0.025 one-sided alpha level) with power specified for the overall design, and the trial stops to either reject or not reject the null hypothesis of the primary objective.

Additional interim analyses may be requested by the DMC, particularly if the first interim analysis is conducted soon after 119 cases of influenza have been reported. In this case, the DMC may request that a second interim analysis be conducted to allow for greater accuracy to determine if the trial should stop or continue.

Table 8.6-1 shows the needed total number of cases at each stage of the two-stage design together with boundaries for early stopping for futility or efficacy, calculated on p-value scale using the cumulative error spending function. With 1/2 information collected at the stage of interim analysis (that is, with exactly 119 confirmed ILIs) the trial would stop early for futility at this stage in case a p-value higher than 0.35022 is observed, or it would stop early for efficacy if the p-value is lower than 0.00625. Otherwise the trial will be continued and more subjects will be enrolled. The actual boundaries used for decision making would depend on number of confirmed ILIs occurring and reported for Interim Analysis.

Table 8.6-1: Example of a Two Stages Group-Sequential Design

	Stage 1 First Interim	Stage 2 Final
Number of Events	119	238
Alpha Boundary on p-value scale (equivalent to Type 1 error, 1-sided), early stopping for efficacy	0.00625	0.02275
Beta Boundary on p-value scale (equivalent to Type 2 error, 1-sided), early stopping for futility	0.35022	0.02275

The stopping rules given above are statistical and should be completed with clinical and strategic stopping rules that allow the DMC to make a decision on a broader picture of the data which includes safety endpoints and the other endpoints of the study. Another interim look at the data with appropriate adjustment of type 1 error might be recommended before reaching the targeted 238 cases.

Further details of the statistical methods are provided in the SAP and more information regarding clinical or strategic stopping rules will be provided in the DMC charter.

For the interim analyses, if needed a restricted unblinding will be done, i.e. only independent DMC members and unblinded individuals responsible for the analyses will receive access to the randomization codes and unblinded data for the purpose of preparing the interim analyses (further information on handling of the blinding for the interim analyses can be found in [Section 3.3](#)). The results of the interim analyses will be used only for DMC purposes and will not be reported in a Clinical Study Report (CSR).

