End of influenza season: The end of the influenza season will be defined as the end of June for Northern Hemisphere (NH) influenza season and end of December for Southern Hemisphere (SH) influenza season. For tropical countries, with no typical NH or SH influenza season, the season is defined by the use of the strains in the vaccine formulation (i.e. strains as recommended for the NH or the SH influenza season) and the timing of vaccination.

Influenza case: An ILI associated with RT-PCR or culture confirmed influenza.

ILI onset: The first day on which a subject fulfils the criteria for protocol-defined ILI.

Medically-attended Adverse Event³: Defined as symptoms or illnesses requiring hospitalization, or emergency room visit, or visit to/by a health care provider.

Modified CDC Influenza-like illness (ILI)⁴: Fever (temperature of $> 37.2^{\circ}\text{C}/99^{\circ}\text{F}$) with cough or sore throat.

Protocol-defined ILI: At least one of the following respiratory symptoms: sore throat, cough, sputum production, wheezing, or difficulty breathing; concurrently with at least one of the following systemic symptoms: temperature of $> 37.2^{\circ}\text{C}/99^{\circ}\text{F}$, chills, tiredness, headache, or myalgia.

Qualified healthcare professional: Any licensed health care professional who is permitted by institutional policy to perform clinical interventions and assessments such as physical examinations and who is identified within the Study Staff Signature Log.

Trained healthcare professional: Any health care professional who is permitted by institutional policy and trained to perform delegated tasks and who is identified within the Study Staff Signature Log.

³ Please also refer to the CRF instructions for further guidance.

⁴ The respiratory symptoms in both definitions are considered a new onset or exacerbation of a pre-existing condition.

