3. STUDY DESIGN

3.1 Overview of Study Design

The study is a phase III, stratified, randomized, observer-blind, non-influenza comparator-controlled, multicenter study to evaluate the efficacy, safety and immunogenicity of an MF59-adjuvanted quadrivalent subunit influenza vaccine compared with a non-influenza comparator vaccine in subjects ≥ 65 years of age.

The study vaccine, aQIV, contains 15 μ g of each of the four seasonal influenza strains (A/H1N1, A/H3N2, B [Yamagata and Victoria lineage]) and MF59 adjuvant. The non-influenza comparator (Boostrix[®]) vaccine will be used to provide a comparative assessment for efficacy, immunogenicity and safety.

Stratification according to age (≥ 65 to 74 and ≥ 75 years), study site and comorbidity status (at risk/not at risk) will be performed (see [Section 5.1.4, Randomization](#) and [Section 5.1.2, Screening](#)). Sample size, among other factors, depends mainly on the number of RT-PCR confirmed influenza cases observed during the influenza seasons, so the overall number of subjects to be recruited provided here may change and enrolment over multiple seasons may be required to ensure 238 PCR-confirmed influenza cases have occurred and/or based on the results of the interim analysis for efficacy and futility.

Nasopharyngeal swab samples will be analyzed in batches and the number of RT-PCR confirmed influenza cases will be reviewed on a regular basis. Once the number of RT-PCR confirmed influenza cases exceeds 119, an interim analysis for efficacy and futility with an appropriate adjustment of the type I error will be performed by an independent Data Monitoring Committee (DMC). Another interim analysis might be recommended before target 238 RT-PCR confirmed influenza cases are observed. Once the number of RT-PCR confirmed influenza cases is ≥ 238 the Sponsor will stop and unblind the trial and perform the final analysis. Stopping rules for futility and efficacy and any additional details regarding the DMC can be found in the DMC Charter.

Each subject will have two stages of study participation: Treatment Period (Day 1 to Day 22) and Follow-up Period (Day 23 to Day 366).

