7.2 Efficacy Assessment

Confirmation of influenza infection by RT-PCR or culture from a nasopharyngeal swab sample is necessary for the efficacy assessment in the study. Nasopharyngeal swab retrieval will be initiated after primary protocol-defined ILI has been identified. Primary protocol-defined ILI can occur at any time during the study and will be evaluated in each subject from Visit 1 (Day 1) through Study Termination. ILI symptoms will be captured during study visits. The ILI onset day is defined as the first day that the subject meets the primary protocol-defined ILI. The end date is defined as the date the last symptom resolves. A new ILI episode will only be taken into account after resolution of the previous one, as judged by the investigator (suggested interval between two ILI episodes is 14 symptom-free days).

Subjects with primary protocol defined ILI will have a NP swab collected for evaluation of the presence of influenza virus. NP swabs should be targeted for collection within 3 days from the ILI onset to ensure optimal viral yield, however samples will be accepted if collected up to 6 days following the day of ILI onset. NP swabs will not be taken beyond a total of 7 days (6 days following onset of ILI) as the level of virus detectable beyond this period can be negligible, particularly for influenza A.

All NP swabs collected from subjects with ILI will be shipped under pre-specified conditions in viral transport media to a qualified lab and stored for analysis for influenza.

NP swabs will be analyzed by RT-PCR and placed into culture. The result of the RT-PCR assay will be the presence or absence of influenza virus. The viral culture will be used for the purpose of viral expansion to enable phenotypic characterization of the influenza virus (e.g. antigenic match). Testing will be conducted by a designated laboratory in a blinded manner towards the treatment arm. Please see the Protocol Ancillary Document for name(s) and details.

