8.1.1.2 Primary Efficacy Endpoint(s)

The primary efficacy endpoint is the time to first-occurrence of RT-PCR-confirmed influenza from 21 through 180 days after vaccination or end of the influenza season, whichever is longer.

The end of the influenza season will be defined as the end of June for Northern Hemisphere (NH) influenza season and end of December for Southern Hemisphere (SH) influenza season. For tropical countries, with no typical NH or SH influenza season, the season is defined by the use of the strains in the vaccine formulation (i.e. strains as recommended for the NH or the SH influenza season) and the timing of vaccination.

An influenza event is defined as RT-PCR- or culture-confirmed influenza infection in the setting of an influenza-like illness (ILI). The primary protocol-definition of ILI will be used to define success for the primary and key secondary efficacy endpoint.

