3. STUDY DESIGN

The study is a phase III, stratified, randomized, observer-blind, non-influenza comparator-controlled, multicenter study to evaluate the efficacy, safety and immunogenicity of an MF59-adjuvanted quadrivalent subunit influenza vaccine compared with a non-influenza comparator vaccine in subjects ≥ 65 years of age.

The study vaccine, aQIV, contains 15 μg of each of the four seasonal influenza strains (A/H1N1, A/H3N2, B [Yamagata and Victoria lineages]) and MF59 adjuvant. The non-influenza comparator (Boostrix[®]) vaccine will be used to provide a comparative assessment for efficacy, immunogenicity and safety.

Approximately 10,692 subjects ≥ 65 years, 5,346 per vaccine group will be randomized to receive either aQIV or non-influenza comparator in a 1:1 allocation ratio, stratifying according to age (≥ 65 to 74 and ≥ 75 years), study site and comorbidity status (at risk/not at risk). Each subject will have two periods of study participation: Treatment Period (Day 1 to Day 22) and Follow-up Period (Day 23 to Day 366). The final study size is based on the number of laboratory confirmed cases of influenza, so that the ultimate number of subjects enrolled will be determined by the actual attack rates of influenza during the conduct of the study. If the number of influenza cases range between 119 and 238, unblinded interim analyses for efficacy and futility will be performed by an independent Data Monitoring Committee (DMC). Once the number of RT-PCR confirmed influenza cases is ≥ 238 the trial will be stopped and unblinded, and the final analysis will be performed. Stopping rules for futility and efficacy and any additional details regarding the DMC can be found in the DMC Charter.

The study procedures consist of four (4) clinic visits (on Days 1, 22, 181 and 366), and three (3) safety phone calls on Days 15, 91, and 271. Subjects participating in the solicited safety subset will receive an additional diary card reminder phone call on day 3.

Additionally, all subjects will receive, at a minimum, weekly phone calls or messages to assess for primary protocol-defined ILI symptoms during the first active ILI surveillance period, defined as from Day 1 through Day 181 or until the end of the regional seasonal influenza season, whichever is longer. The purpose of the ILI surveillance phone calls/message is to trigger a clinic or home visit to collect a nasopharyngeal swab.

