- If the number of first-occurrence RT-PCR confirmed influenza cases from 21 through 180 days after vaccination or until the end of the influenza season, whichever is longer, is greater or equal to 120 but less than 238 unblinded interim analyses for efficacy and futility will be performed by the DMC (see below for description).

- If the number of first-occurrence RT-PCR confirmed influenza cases from 21 through 180 days after vaccination or until the end of the influenza season, whichever is longer, is greater or equal to 238 (targeted number of cases to be able to evaluate the primary objective) the trial will be stopped, data will be unblinded and the final analysis will be performed by the Sponsor. If the trial proceeds to the final analysis (upon reaching 238 cases) the boundaries for acceptance or rejection are identical to the assumed type 1 and type 2 errors for the overall design, and the trial stops to either reject or not reject the null hypothesis of the primary objective. That is, the primary objective, i.e. VE against RT-PCR confirmed influenza A and or B will be assess the one-sided 0.025 alpha level.

If the DMC states that the observed data provides already the full information level needed for the final test decision, then the final analysis can be done on full alpha level of one-sided 0.025 and no further enrollment is needed. However if the decision of the group-sequential test is to continue the study then it is on the DMC to determine the number of subjects needed to be additionally enrolled. The DMC should not be influenced by the results of the efficacy testing at the interim analysis when planning further subjects' accrual or the times of future analysis. Only the overall number of cases is allowed to be used for further planning. The following formula for determination of sample sizes for further enrollment may be used:

$$N_{\text{total}} = (C_{\text{planned}} - C_{\text{observed}}) / ER,$$

where N_{total} denotes the total number of subjects needed for further enrollment, C_{planned} is the overall number of cases needed for the test, i.e. 238 cases, C_{observed} is the number of cases observed at current stage, and ER is the observed total attack rate for both groups combined. A drop-out rate of 10% should be added.

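### The 119/238 case count that triggers the interim and ends the trial is limited to primary-endpoint cases in SAP 14.1 and 15, but has no such limit in the protocol or SAP 3

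*Protocol*

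**What the plan says.** **The primary event.** Protocol 8.1.1.2: "The primary efficacy endpoint is the time to first-occurrence of RT-PCR-confirmed influenza from 21 through 180 days after vaccination", or to season end if that is later. SAP 2.1.2 agrees. The sample-size sections (protocol 8.5, SAP 5) attach the 238 events and 86.5% power to first-occurrence RT-PCR-confirmed influenza.

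**The open count.**
- Protocol 3.1 (and the synopsis), interim: "Once the number of RT-PCR confirmed influenza cases exceeds 119, an interim analysis for efficacy and futility".
- Protocol 3.1 (and the synopsis), stop: "Once the number of RT-PCR confirmed influenza cases is ≥ 238 the Sponsor will stop and unblind the trial".
- Protocol 3.6 and 3.7 use RT-PCR-confirmed cases between 119 and 238, also without a window.
- Protocol 8.6 uses RT-PCR-confirmed cases in its first bullet and plain influenza cases in the next two, including the stop rule: "If the number of influenza cases is greater or equal to 238 (targeted number of cases to be able to evaluate the primary objective"). Elsewhere 8.6 speaks of ILI-cases and confirmed ILIs.
- SAP 3, interim: "If the number of influenza cases range between 119 and 238, unblinded interim analyses for efficacy and futility will be performed". Its stop rule is 238 RT-PCR-confirmed cases, again without a window.
- Protocol Definitions: "Influenza case: An ILI associated with RT-PCR or culture confirmed influenza".

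**The restricted count.** SAP 14.1 bases all three of its rules on this quantity: "number of first-occurrence RT-PCR confirmed influenza cases from 21 through 180 days after vaccination or until the end of the influenza season" (the later of the two end points applies). SAP 15 repeats this for the interim.

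**Surveillance.** Protocol 7.2 says that protocol-defined ILI "can occur at any time during the study and will be evaluated in each subject from Visit 1 (Day 1) through Study Termination". Protocol 3.9 allows swabs up to Day 366. Protocol 7.2 also recognises a new ILI episode in the same subject once the previous one has resolved.

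**The concern.** One threshold is attached to two counts. The open count can include cases on Days 1 to 20, cases after Day 180 or season end, and second cases in the same subject. Where the text says only influenza cases, it can also include culture-only cases. None of these is a primary event. The plan itself expects some cases before Day 21, because secondary efficacy objective 4 starts at Day 7.

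Two decisions depend on the count. At 119 it opens the unblinded interim, which is meant to sit at half the planned information. At 238 it stops and unblinds the trial, and that cannot be reversed. If the open count is applied, the primary Cox model may hold fewer than the 238 events that the power statement assumes. The same count enters the re-enrolment formula as C_observed, so a loose count would also make further enrolment too small.

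**Working it through.** **Inputs**
- VE 60% (HR 0.4), margin 40% (HR 0.6), 238 events, 1:1 allocation, one-sided 0.025, stated power 86.5%: protocol 8.5, SAP 5.
- Boundaries at 119 events: efficacy p < 0.00625, futility p > 0.35022. Boundary at 238 events: 0.02275. Source: protocol Table 8.6-1, SAP 14.1 Table 1.
- Share f of counted cases that are not primary events: not in the documents. Assumed values 0% to 20%.

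**Step 1: event target.** 4,860 × (0.035 + 0.014) = 238.1. The 238 is therefore a count of events at the attack rates assumed for the primary endpoint.

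**Step 2: reproduce the stated power.** With D events and equal-allocation variance 4/D, the mean of the test statistic is ln(0.6/0.4) × √(D/4) = 0.4055 × √D / 2.
- Fixed design, one-sided 0.025: Φ(3.128 − 1.960) = 87.9%.
- Two-stage design: means 2.212 at 119 and 3.128 at 238, correlation √(119/238). Critical values are 2.498 (efficacy, stage 1), 0.385 (futility, stage 1) and 2.000 (final). Power = P(Z₁ > 2.498) + P(0.385 < Z₁ < 2.498, Z₂ > 2.000) = **86.45%**. The type I error of the same calculation is 0.0250.

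The two-stage result matches the stated 86.5%, and it takes all 238 to be primary events.

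**Step 3: stop at 238 counted cases when a share f is not primary.** Primary events at the final are 238 × (1 − f) and at the interim 119 × (1 − f). The information fraction at the interim, relative to 238, is 0.5 × (1 − f). Power is recalculated as in Step 2, holding the tabulated p-value boundaries and the half-way interim.

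| f (assumed) | Primary events at final | Primary events at interim | Interim information fraction | Two-stage power | Counted cases needed for 238 primary, 238/(1 − f) |
|---|---|---|---|---|---|
| 0% | 238 | 119 | 0.500 | 86.5% | 238 |
| 2% | 233 | 117 | 0.490 | 85.8% | 243 |
| 5% | 226 | 113 | 0.475 | 84.7% | 251 |
| 10% | 214 | 107 | 0.450 | 82.7% | 264 |
| 15% | 202 | 101 | 0.425 | 80.6% | 280 |
| 20% | 190 | 95 | 0.400 | 78.2% | 298 |

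Power uses the unrounded event number; at exactly 202 events it is 80.5%. It stays within 2 points of the plan for f up to 5% and falls below 80% between 15% and 20%.

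**Step 4: re-enrolment.** The protocol 8.6 formula adds 200/(1.4 + 3.5) = 40.8 subjects per outstanding case. Each non-primary case left in C_observed therefore removes about 41 subjects from planned further enrolment, before the 10% drop-out allowance. The SAP 14.1 formula also subtracts C_observed, so the direction is the same.

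**The case against.** The best defence is that the correct count is already in the operative text. SAP 14.1 and 15 state it exactly, protocol 8.6 refers to the SAP for further statistical detail, and SAP 3 is a design summary. The protocol never says that cases of any timing count: its stop rule ties 238 to the primary objective, section 2.1 limits the efficacy objectives to the window, and Table 8.6-1 labels the numbers as events. If SAP 14.1 is followed, no shortfall arises. This stands as evidence of intent. It does not settle the matter, because SAP 3 repeats the open rule within the SAP itself, and the rule concerned irreversibly stops and unblinds the trial.

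A reader might infer more than the documents support:
- *That the trial will stop short.* This happens only if the open wording is applied and non-primary cases occur in the count. The rule is 238 or more and swabs are tested in batches, so the count may also overshoot.
- *That culture-only cases count everywhere.* They enter only through the Definitions, where the text says influenza cases: the later bullets of protocol 8.6 and the SAP 3 interim sentence. The stop rules in the synopsis, protocol 3.1 and SAP 3 all say RT-PCR.
- *That power is far below plan.* A variance using the case split expected at VE 60% (68 and 170) gives Φ(0.4055/√(1/68 + 1/170) − 1.96) = 80.7% with all 238 events. That approximation does not reproduce 86.5%, so setting its results against 86.5% would blame the case count for a gap that comes from the formula.
- *That type I error is inflated, or that an early interim is invalid.* Both documents base the interim boundaries on the information actually accumulated, and SAP 14.1 asks only for approximately 50%.

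**Conclusion.** The inconsistency is real and is in the current text of both documents. SAP 14.1 and 15 carry the count that matches the primary endpoint and the power calculation. The protocol synopsis, 3.1, 3.6, 3.7 and 8.6 and SAP 3 carry a looser one. Under the looser rule, the trial can stop with fewer than 238 primary events.

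The size depends wholly on f, which the documents do not give. The loss is under 1 point at 2%, about 2 points at 5%, 4 at 10% and 6 at 15%, on the calculation that reproduces the plan's own figure. The loss is modest at the low end of the range. The correction should still be made, because the decision cannot be undone and the change costs almost nothing.

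**What to change.** Use the SAP 14.1/15 count wherever 119 or 238 governs a decision: protocol synopsis, 3.1, 3.6, 3.7 and 8.6, and SAP 3. Apply it to C_observed in both re-enrolment formulas, and replace the ILI-cases and confirmed-ILIs wording in protocol 8.6 and SAP 14.1. State that cases before or after the window, repeat cases in a subject and culture-only cases do not count towards 119 or 238.

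One further suggestion goes beyond what SAP 14.1 says: specify that window membership is judged by ILI onset date, among subjects in the Efficacy FAS.

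The cost is wording in two documents and an onset-date and first-occurrence filter in the blinded case count. The target, test and endpoint do not change. The downside is that the trigger may be reached slightly later; under the assumed shares of 2% to 15%, that means waiting until about 243 to 280 cases on the loose count.
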